Official Title: ICU experience among family members of ICU patients

NCT #: NCT02940028

Document Date: May 28 2020

Protocol

Title:	ICU experience among Family Members of ICU Patients
Location of Research:	Intermountain Medical Center
Principal Investigator:	[name]
Sponsor:	Intermountain Research and Medical Foundation
Study Team:	[name] [name] [name] [name] [name] [name] [name]

Purpose of the Study:

The purpose of this study is to investigate whether an expressive writing intervention increases post-traumatic growth (PTG) in family members of patients admitted to the ICU with a serious illness and explore the association between coping phenotypes and PTG. PTG will be compared between the intervention group receiving the expressive writing intervention and the control group (non-expressive or fact-based writing). The primary outcome will be PTG at 12 weeks, with secondary outcomes of depression, anxiety and posttraumatic stress disorder (PTSD) at follow up.

Hypothesis/Research Questions:

In two hypotheses evaluated in two specific aims, we will investigate whether an expressive writing intervention increases PTG in family members of patients admitted to the ICU with a serious illness and explore the association between coping phenotypes and PTG. PTG will be compared between the intervention group receiving the expressive writing intervention and the control group (non-expressive or fact-based writing). The primary outcome will be PTG at 16 weeks, with secondary outcomes of depression, anxiety and PTSD at follow up.

Specific Aim 1: Examine the association between participating in an expressive writing intervention and development of post-traumatic growth.

Primary outcome: Post-Traumatic Growth Inventory at 4 months

Secondary outcomes: Impact of Events Scale-Revised (IESR), Hospital Anxiety and Depression Inventory (HADS) at 4 months

Hypothesis 1a: Participants in the intervention group will have higher levels of post-traumatic growth at follow-up than participants in the control group.

Hypothesis 1b: Participants in the intervention group will have lower PTSD, depression, and anxiety scores at 4 months.

Specific Aim 2: Explore whether individual coping phenotypes predict PTG. Predictors for consideration include acute perceived stress (Perceived Stress Scale-4 [PSS-4], personality characteristics (Big Five Inventory [BFI]) coping ability (Brief COPE), social relationship quality (Social Relationship Inventory (SRI abbreviated), measures of disability in activities of daily living and instrumental activities of daily living caregiver burden (Groningen Activity Restriction [GARS] Scale), patient age and severity of illness (APACHE score).

Hypothesis 2a: ICU families coping phenotypes (stress, personality characteristics, and coping) will be associated with PTG.

Hypothesis 2b: Other variables related to the ICU (APACHE IV score, age, sex, ethnicity, whether the patient dies before follow-up) and post-ICU (care giver burden) experience will be associated with PTG at 3 mos.

Background and Significance:

Post-ICU psychological distress is common and important

The intensive care unit (ICU) is a stressful and challenging place for patients and their families, who must navigate illness and its associated discomforts as well as complex decision making in an environment characterized by tremendous uncertainty¹⁻³. Negative emotions including stress, fear, anger, and fatigue are extremely common during an ICU admission^{4,5}. Many family members experience anxiety, depression, and posttraumatic stress disorder (PTSD) during and after the ICU experience that persists years after their loved one is discharged from the ICU^{3,6-8}.

During an ICU stay, it is common for patients to be too ill to participate in decision making in the ICU⁹ – and medical decision making will generally be made by the family members designated surrogate decision makers⁷. Surrogate medical decision making may be intense and stressful and may contribute to development of anxiety, depression and posttraumatic stress disorder (PTSD) in family members³.

Persistent psychological distress after ICU admission is part of a recognized syndrome called post-intensive care syndrome-Family (PICS-F)¹⁰. The reasons for PICS-F in response to the emotional trauma of the ICU are multifactorial, and include pre-existing risk factors, failures to meet informational needs, threat of death or serious disability, and decision-related stress, given the heavy psychological burden associated with decision making about matters of life and death^{1,3}. Traumatic experiences, however, can also result in positive psychological outcomes – including better relationships, improvements in spiritual well-being, greater self-efficacy, and personal development. Such positive post-trauma outcomes are known as post-traumatic growth (PTG)¹¹ and may represent an alternative to the PTSD and anxiety that have come to the hallmark of PICS-F.

Post-traumatic growth

Post-traumatic growth is a positive change in a person's sense of self that is part of a complex narrative or personal life story that occurs after a difficult life experience. An individual's world view with the accompanying goals, beliefs, and habits of managing emotional feelings and stress can be shaken by traumatic experiences and then, over time, are rebuilt into a new positive view of the self and life¹¹⁻¹³. Post-traumatic growth (PTG) has been observed in response to a wide variety of traumatic experiences including medical illnesses (chronic illness, cancer, AIDS), military combat, man-made disasters (e.g., shootings) and natural disasters (e.g., tornadoes)^{14,15}. Patterns of PTG vary based on aspects of the trauma and the individual's characteristics. Some evidence suggests that the traumatic events associated with the greatest PTG represent intermediate levels of harm. Personal characteristics associated with PTG, include openness, extraversion, agreeableness and conscientiousness alternatively neuroticism is associated with less PTG. Greater PTG is associated with -focused coping and cognitive processing of the traumatic event, involvement in religious activities and high levels of perceived social support¹⁵⁻¹⁷. Overall, some degree of emotional processing of the traumatic event must take place for PTG to occur,¹² and such processing is most likely to result in post-traumatic growth in a particular personal and social context.

Post traumatic growth takes time to emerge, with most positive changes occurring within 2 months after the trauma¹⁸ while the level of PTG remains stable 3 to 8 years following the trauma^{19,20}.

Potential Benefits of Expressive Writing

Although PTG is a naturally occurring process, deliberate interventions can increase its likelihood. Some interventions are time-consuming and expensive – such as cognitive behavioral therapy. But, in some contexts, interventions centered on a specific type of journaling known as “expressive writing” have increased PTG. Semi-structured expressive writing was developed by [name]. as a structured technique for recording deep thoughts and feelings about a traumatic event in a structured setting²¹. Expressive writing facilitates coping with trauma by helping people process – emotionally and cognitively – a traumatic event. Participating in expressive writing – commonly three 20-minute sessions on three consecutive days – includes writing about emotions and thoughts associated with the traumatic event. Variations include providing participants with a journal and asking them to complete the writing at set times at home²² or using an internet-based journal²³. In many studies expressive writing interventions are associated with improved outcomes including fewer reports of physical symptoms, a reduction in PTSD and greater PTG²²⁻²⁴. In addition, expressive writing is associated with reduced healthcare utilization, fewer physical symptoms, and fewer PTSD symptoms on follow-up^{21,22,25}.

Family members and patients enter the ICU with unique characteristics that may affect their risk for psychological distress²⁶. In other trauma-exposed populations, individual attributes have been associated with development of PTSD^{26,27}. Personalizing the experience of family members by offering post-ICU support strategies, such as writing interventions, may decrease psychological distress and improve positive outcomes and PTG^{11,28}.

[figure not shown]
In prior work, we identified ICU family member coping phenotypes that would identify individual attributes, preferences, and vulnerabilities (personality dimensions, shared decision-making preferences, coping styles, and social support) that might be relevant to the experience of ICU surrogates²⁹. We identified three copying phenotypes including adaptive copers, maladaptive copers, and disengaged copers. Coping phenotypes differed primarily on coping styles, personality, quality of their closest social relationship, and history of anxiety and depression.²⁹ Early work suggests that individuals in certain coping phenotypes may have different approaches to surrogate decision making and different satisfaction with the shared decision making during a simulated ICU experience. They may also have different probabilities of PTG.

Research Subjects:

Inclusion Criteria:

Family members of ICU patients are eligible for the study. We will enroll **one** study participant per patient admitted to a study ICU (Shock Trauma or Respiratory ICU at Intermountain Medical Center) who meets the following inclusion criteria:

- Participant can be a family member of a patient admitted to a study ICU for >24 hours and ≥ 1 of the following:
 - mechanical ventilation via endotracheal tube for ≥ 12 hours
 - non-invasive ventilation (CPAP, BiPAP) for > 4 hours in a 24-hour period provided for acute respiratory failure in an ICU (not for obstructive sleep apnea or other stable use)
 - high flow nasal cannula or face mask O₂ with FiO₂ ≥ 0.5 for ≥ 4 hours
 - use of vasopressors for shock of any etiology for >1 hour
- The priority for enrollment is outlined in the picture below.

* A default surrogate can include (in order of preference):

- | | |
|---|-----------------------|
| 1. Spouse (unless divorced or legally separated OR if court finds spouse acted in a manner that should preclude him/her from having a priority position) | 2. Adult child |
| | 3. Parent |
| | 4. Sibling |
| | 5. Grandparent |
| | 6. Grandchild |

- Both participant and ICU patient must be adult (age ≥ 18 years of age)
- Participant must be able to read, speak, and write in English
- Participant must be enrolled within 72 hours of the patient's meeting mechanical ventilation criteria.

Participants who live with the patient will be accorded higher priority than those who do not live with the patient because they are more likely to be involved as caregivers. The preference would be for the

participant to be the designated power of attorney; if there is no designated power of attorney living with the patient, then the primary informal caregiver (identified either by the patient or by the family) would be enrolled; if either of these is not available, the default surrogate (defined in figure 1) would be enrolled. If no one living with the patient meets these criteria, then family members and informal caregivers not living with the patient will be screened for the study. The preference would again be for first, the designated power of attorney, then a primary caregiver and a default surrogate. An informal caregiver provides care without reimbursement.

Participant Exclusion Criteria:

- Pregnant or breastfeeding females
- Prisoners
- Children (age <18 years of age)
- Known history of PTSD, dementia, or schizophrenia. Presence of these illnesses will be per participant report of physician diagnosis and treatment
- If a patient has been transferred from another ICU after an ICU course greater than 24 hours, or if the patient has had a previous ICU or long-term acute care (LTAC) admission in the last 90 days, the family member or caregiver will be excluded.
- Patients admitted for hospice
- Participants who live more than 200 miles away or who have no specified domicile
- Non-English speaking

Because ICUs are sometimes used for simple monitoring of patients with low severity of illness and that experience is likely to be quite different from an admission for critical illness, we restrict to patients with at least a moderate severity of illness as judged by >48 hours of mechanical ventilation. We exclude participants who have underlying mental disease such as PTSD, dementia, and schizophrenia because these participants may process trauma-related information very differently from other participants. The intervention features expressive writing so understanding, speaking, and writing in English is critical as we will not have the capacity to conduct data analysis of the writing sample in other languages. We are most interested in subjects who have experienced acute stress at an identifiable time (during the ICU admission) thus family members who have already been in ICU or in other critical care environments may not be undergoing acute stress.

Recruitment:

Qualified study participants will be consented prior to commencing any research-related activity. These individuals will be approached in the patient's room or waiting room in the ICU or by telephone.

Methods/Procedures: Baseline Assessment

Participants will be enrolled in the study if they meet study inclusion and no exclusion criteria and signed informed consent. Participants will be administered baseline questionnaires, randomly assigned to the intervention or control condition, participate in intervention or control writing condition at 4 weeks (range 2 to 8 weeks) after enrollment, and administered follow-up questionnaires at three months after the writing intervention (\pm 2 weeks) by telephone.

Questionnaires

Participants will complete baseline questionnaires including³², PSS-4, BFI, Brief COPE, HADS and the IESR.

Table 1. Questionnaires administered at study enrollment

Instrument	Measures	Scale	Scoring
Hospital Depression and Anxiety Scale	Depression and anxiety	14 items (7 each for anxiety and depression). Items scored 0 to 3. Total scores for each scale range from 0 to 21.	Scores of 8 or higher indicate symptoms or depression or anxiety. ³³
Impact of Event Scale Revised (IES-R)	Screens for PTSD	22-item scale measuring intrusion, avoidance and hyperarousal; each item scored from 0-4	A mean score of ≥ 1.6 indicates PTSD symptoms. ^{34,35}
Perceived Stress Scale	Feelings of stress	4 items with scores that range from 0 to 4	Higher scores indicate greater stress. ^{36,37}
Brief COPE	Coping with stress	14 dimensions with 2 questions per dimension	Higher scores indicated greater use of a given coping strategy. ³⁸
Social Relationship Inventory (abbreviated)	Quality of Social Support	3 dimensions of relationship for the person closest to the respondent, helpfulness, upset, and unpredictability rated from 1 (not at all) to 6 (extremely)	Higher scores on each dimension indicate greater helpfulness, upset, and unpredictability.
Big Five Inventory	Personality dimensions: openness to new experiences, conscientiousness, extraversion, agreeableness and neuroticism.	10 items	Higher scores indicate greater degree of a specific personality characteristic. ³⁹

Random Assignment and Intervention

Random assignment to condition will be completed using random number generator. Participants will receive instructions for participating in the intervention.

The intervention will take place in person at 4 weeks (± 2 to 8 weeks). Participants will participate in a semi-structured 20-minute expressive writing session in person or at home with instructions. For those in the experimental expressive writing condition, the instructions (adapted from Stanton & Danoff-Burg)²⁴ will be:

“What I would like you to write about for these three sessions are your deepest thoughts and feelings about your experience with your family member in the Intensive Care Unit (ICU). I realize that people with a loved one in the ICU experience a full range of emotions and thoughts, and I want you to focus on any and all of them. In your writing, I want you to really let go and explore your very deepest emotions and thoughts. You might think about all the various feelings and changes that you experienced before your loved one was hospitalized in the ICU, after the diagnosis that led them to the ICU, during treatment, and now. Whatever you choose to write, it is critical that you really focus on your deepest thoughts and feelings. Ideally, I would like you to focus on feelings, thoughts, or changes that you have not discussed in great detail with others-private feelings. You might also tie your thoughts and feelings about your experiences with having your loved one in the ICU to other parts of your life, i.e., your childhood, people you love (this loved one and others), who you are, or who you want to be. Again, the most important part of your writing is that you really focus on your deepest emotions and thoughts. The only rule we have is that you write continuously for the entire time. If you run out of things to say, just repeat what you have already written. Don’t worry about grammar, spelling, or sentence structure. Don’t worry about erasing or crossing things out. Just write.”

Participants in the control condition will receive the following instructions:

“What I would like you to write about for these three sessions are all the facts about your experience with your family member in the Intensive Care Unit (ICU). We are not interested in your thoughts and emotions. Please do not include them. We are interested in all the facts about how your loved one came to the ICU and the facts about your experiences in the ICU with your loved one. The only rule we have is that you write continuously for the entire time. If you run out of things to say, just repeat what you have already written. Don’t worry about grammar, spelling, or sentence structure. Don’t worry about erasing or crossing things out. Just write.”

Participants will write for 20 minutes for 3 sessions that will occur over a 2-hour period on the participation day (8 weeks after the hospitalization). Participants who are comfortable typing will type responses into a REDCap website via a tablet and keyboard which will measure the amount of time spent writing or at home on their computer and will email the writing sample to the study coordinator.

Participants who use handwriting will be observed by the project coordinator if in person. Instructions will be sent to the participant if completing the writing at home.

- a. Study coordinator will call the study participant to assess if they are willing and able to do the writing at home and set up a date and time for them to do the writing follow-up at home.
- b. Each participant will be sent a unique identifier (ex. 193JTA) that we will link to study ID and them they will be instructed use the code to identify their writing instead of their name.
- c. An instruction sheet will be emailed or sent to the participant via email or regular mail if writing long hand.
- d. The participants will be instructed to use the identifier in the subject line of email when they send the writing sample back to the study coordinator [name] at [contact] or to [name] at [contact].

- e. If writing is done long-hand a self-addressed stamped envelope will be included to send back the writing to the study coordinator.

Manipulation checks include completion of the Essay Evaluation form in which participants will rate how personal, meaningful, and reflective of their feelings their essay is. Participants in the control condition should rate this very low in comparison to participants in experimental conditions. All participants who complete follow up will receive a gift card after completing the writing intervention.

4 Month Follow-up

Four months after the writing exercise, participants will be contacted to complete an instrument battery by telephone. Follow-up measures include IES-R, HADS, PSS-4, Groningen Activities Restriction Scale (GARS) for assessing impact of the traumatic event on functional and emotional health and Posttraumatic Growth Inventory (PTGI). Following participation participants will receive gift card payment in the mail.

4 Month Follow-up			
Hospital Depression and Anxiety Scale	depression and anxiety	14 items (7 each for anxiety and depression). Items scored 0 to 3. Total	Scores of 8 or higher indicate symptoms or depression or anxiety. ³³
Impact of Event Scale Revised (IES-R)	Screens for PTSD	22-item scale measuring intrusion, avoidance and hyperarousal	A mean score of ≥ 1.6 indicates PTSD symptoms. ^{34,35}
Perceived Stress Scale	Feelings of stress	4 items with scores that range from 0 to 4	Higher scores indicate greater stress. ^{36,37}
Brief COPE	Coping with stress	14 dimensions with 2 questions per dimension	Higher scores indicated greater use of a given coping strategy. ³⁸
Post-Traumatic Growth Inventory	Positive perceptions of change following a traumatic event	21 items that use a 6 point Likert scale (0-5)	Higher Scores Indicate greater PTG
Physical Symptoms Inventory – 13 Item Version	Examines physical symptoms experienced during previous 30 days adapted to include medical utilization	13 items that use a 5 point Likert Scale (1-5)	Higher scores indicate more symptoms on more days. ^{21,24}

Groningen Activity Restriction Scale (GARS)	Assess degree of restriction experienced due to providing care in 11 categories: caring for him/herself, caring for others, eating habits, shopping for him/herself, visiting friends, working on hobbies, sports and recreation, going to work, and maintaining friendship. Developed and used in ICU populations, ⁴⁶⁻⁴⁹ shopping for him/herself, visiting friends, working on hobbies, sports and recreation, going to work, and maintaining friendship. and used in ICU populations. ⁴⁶⁻⁴⁹	11 items scored from 1 to 4	Scores range from 11 to 44 with higher scores indicating greater activity restriction.
Groningen Activity Restriction Scale (GARS)	Assess degree of restriction experienced due to providing care in 11 categories: caring for him/herself, caring for others, eating habits, sleeping habits, doing household chores, going	11 items scored from 1 to 4	Scores range from 11 to 44 with higher scores indicating greater activity restriction.
Essay Evaluation Measure	Perception that essay was personal, meaningful and revealing of their emotions	Each item Likert 0-6 total range 0-18	Higher scores indicate that participants found the essay personal and meaningful and revealing of their emotions (0-18) ⁵⁰
Evaluation of essays not done with participant			

Informed Consent:

Study-designated Intermountain Healthcare employees (either the research coordinator(s) or the study investigator(s)) will obtain informed consent from the study participant. The study staff member obtaining consent will provide the participant with the current IRB-approved Informed Consent Form and will be available to answer any questions the participant may have. Individuals approached for consent will be given as much time as they require to consider enrollment in the study.

The ICU patient will not be approached or questioned. They are indirectly involved, as the study participant is defined by their relationship to the patient. Minimal information will be obtained about the patient from the medical record to allow assessment of the effects of acute severity of illness or length of stay. The ICU patient will not be consented as they are not the subject of the study and minimal information is collected regarding these individuals. We will ask for a waiver of informed consent to gather this data.

Waiver of Informed Consent

The ICU patients are not directly involved and will not be approached or questioned. Minimal information will be obtained about the patients. The ICU patients will not be consented as they are not the subject of the study and minimal information is collected regarding these individuals. We will ask for a waiver of informed consent to gather this data. We feel it is not necessary or appropriate to obtain consent from the ICU patients for these reasons.

Only the minimum PHI needed will be collected. We will only collect names, hospital ID number and dates necessary to determine hospital and length of ICU stay. The study data will be stored on secure computers and will be de-identified. We will protect confidentiality and privacy in a HIPAA- and Good Clinical Practice- compliant way. Subjects will be given an anonymous study ID. In addition to managing only non-identified data, we will also protect that data by storing it only on secure computers. The only data sharing will be with our collaborator [name] at the University of Utah. All other data sharing such as might be required for regulatory reasons or to comply with editorial requirements of scientific journals, will be deidentified.

Risks:

Based on prior research in psychology and in critical care, we anticipate that there will be only minimal risk to those participating in this research. Patients may experience some discomfort from answered survey questions and writing about their family members ICU experience. In our experience surveying many hundreds of patients and families during and after an ICU admission, this is very uncommon. Participants are always free to decline to answer any question or further participation. Breach of confidentiality is a potential risk, but the data will be appropriately safeguarded against inappropriate disclosure.

Benefits:

Data indicate that ICU admission results in adverse psychological outcome including depression, anxiety and posttraumatic stress disorder. If the intervention enhances PTG, we will be able to help family members of critically patients develop positive outcomes. Our ultimate goal is to understand, predict, and improve psychological outcomes (depression, anxiety and PTSD) in patients and their family members after ICU admission. This study may help future ICU patients and their family members by helping us to understand how PTG may affect psychological wellbeing for family of patients admitted to the ICU

Impact on Intermountain

Intermountain Medical Center is a pioneer in the study of long-term outcomes after critical illness and patient- and family-centered intensive care. We plan to expand these investigations into a better understanding of the long-term outcomes and acute patient- and family-related experiences associated with an ICU admission more generally. This work will allow us to expand prior expertise and reputation in the field of long-term outcomes after critical illness and to establish Intermountain Medical Center as a leader in interventions during critical illness that improve long-term outcomes. We see this research project as a key way to further cement Intermountain's profound leadership in creating ICUs that are carefully attuned to the human side of serious illness.

Compensation:

If participants decide to participate in the study, to compensate them for their time and effort, at the writing exercise visit, they will receive a \$50 gift card or be mailed a \$50 check. After the 4-month follow-up phone call, they will receive another \$50 gift card or be mailed a \$50 check. Thus, if they complete the study, they will receive a total of \$100 for the two visits.

Data Collection:

Demographic Characteristics: Participant age, sex, ethnicity, years of educational attainment, identification with religion (e.g., Buddhism, Christian, Muslims well as “Spiritual but not religious” or “other”) were collected. The importance of religion was assessed using the following questions: (*How important is religion in your daily life?*) from (1) *not at all* to (4) *extremely* and religious service attendance (*How frequently do you attend religious services?*). History of anxiety and depression were assessed (e.g., *Do you have a personal history of anxiety?*), and whether they had ever received treatment by a physician or mental health provider.

This study requires the use of the following information:

- ICU Patient information (the only PHI required is the hospital ID number used to collect the non-PHI demographics and outcome information)
 - Age (if the patient’s age is greater than 89, it will be recorded as 89)
 - Sex
 - Race
 - Ethnicity
 - Primary ICU diagnosis
 - APACHE II score at admission
 - Prior ICU admissions in the last 5 years (per report from participant)
 - Mortality at 3 months (i.e., living or deceased per report from participant)
 - Hospital and ICU length of stay
 - Presence of mechanical ventilation
 - Baseline terminal illness (congestive heart failure, ESRD, liver failure, cancer)

- Study Participant information:
 - Age
 - Sex
 - Race
 - Ethnicity
 - Religion (importance, affiliation, and degree of importance)
 - Employment status
 - Number of hours weekly spent with the patient (averaged over the last month) and whether the participant lives with the patient,
 - Highest level of education.
 - Limited medical history: diagnosed depression, anxiety, sleep disorder, obesity. ^{30,31}
 - Psychiatric history of depression or anxiety
 - History of substance and alcohol abuse

The informed consent form describes the elements of PHI that will be used as a part of this study. All identifiable study information that is collected will be kept on computers owned and secured by Intermountain Healthcare. Any PHI collected for this study will be de-identified prior to disclosure to study collaborators outside of Intermountain Healthcare and only under authorization of current, valid data use agreements. The code used to de-identify these subjects will be retained by the Intermountain Healthcare Principal Investigator to allow re-identification of the subject should clarification of information be required. Identifiers of study participants will be maintained securely in order to report study results to participants, e.g., via newsletters.

We will randomize family members to receive either the PTG intervention and or non-intervention control group (control writing condition). The intervention group will participate in a brief expressive writing intervention. The control group will receive a control writing condition (fact-based writing) and complete the other study measures.

Descriptive statistics will be calculated for all demographic variables as well as all instruments (both at baseline and 4 month follow up). PTGI at 4 months (along with the secondary outcomes) will be compared between the intervention and control arms using Wilcoxon Rank Sum tests. Further, we will use linear regression to assess the relationship between expressive writing and PTGI at 4 months, adjusting for other relevant factors (i.e., participant demographics, (including age), patient demographics, illness severity of the patient, social support of the participant, caregiver burden, etc.).

Sample Size:

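### The only outcome call is timed from the writing, which follows randomisation, and no rule covers randomised participants who do not write

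*Protocol*

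**What the plan says.** Under Methods/Procedures: Baseline Assessment, participants complete baseline questionnaires and are then "randomly assigned to the intervention or control condition, participate in intervention or control writing condition at 4 weeks (range 2 to 8 weeks) after enrollment". The writing is therefore a post-randomisation event. The same sentence has them "administered follow-up questionnaires at three months after the writing intervention". The 4 Month Follow-up section gives a different interval but the same starting point: "Four months after the writing exercise, participants will be contacted to complete an instrument battery by telephone". The PTGI is collected only at this call.

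Elsewhere the time point has no starting event. Specific Aim 1 has "Primary outcome: Post-Traumatic Growth Inventory at 4 months", and Hypothesis/Research Questions has "The primary outcome will be PTG at 16 weeks". The analysis paragraph at the end of Data Collection says that PTGI and the secondary outcomes "will be compared between the intervention and control arms using Wilcoxon Rank Sum tests"; it does not limit this to people who wrote.

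The protocol foresees that some people may not write. In the home-writing steps under Random Assignment and Intervention, "Study coordinator will call the study participant to assess if they are willing and able to do the writing at home", and the same step agrees a date and time. The Risks section adds: "Participants are always free to decline to answer any question or further participation". No section says what happens to the telephone follow-up when a randomised participant declines the writing, stops, or never returns it.

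**The concern.** Aim 1 compares randomised arms, but the trigger for measuring the outcome is something a participant does after randomisation. Under the rule as written, someone who does not write never reaches the date on which the call falls due.

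Willingness to write could differ by arm, because one set of instructions asks for private emotion and the other asks for facts with emotion left out. It could also be related to the outcome. The Background section says that growth requires some emotional processing of the trauma, and the IES-R includes avoidance items. People who avoid the task may therefore differ on PTGI and IES-R from those who complete it.

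The call itself needs no essay. The IES-R asks about the ICU stay, the HADS about the past week and the PTGI about the respondent's crisis. This is a matter of study conduct rather than analysis: a statistical analysis plan can define who is analysed, but it cannot supply a PTGI score that nobody collected.

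**Working it through.** **1. The plan's own sample size.** Inputs from Sample Size: means 45 and 56 (difference 11), alpha 0.05, Wilcoxon test, 102 evaluable, 130 enrolled at 65 per arm. The raised figures 18 and 21 are read as SDs because the text introduces them as mean (SD). Two-sided testing and 80% power are assumed, since neither is stated.

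- Common SD = √((18² + 21²)/2) = √382.5 = 19.56.
- n per arm = 2 × (19.56 × (1.960 + 0.842)/11)² = 49.6, so 50 per arm and 100 in total.
- Dividing by the Wilcoxon efficiency 3/π = 0.955 gives 52 per arm, 104 in total.

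The stated 102 lies between these, so it is reproduced. The allowance for loss is (130 − 102)/130 = 28/130 = 21.5%. It is not split between non-writers and people lost for other reasons, and it protects the sample size, not against selective loss.

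**2. Bias if only writers are measured.** Let q be the non-writing fraction in an arm and d the PTGI gap, writers minus non-writers. If the mean of all randomised is μ, then μ = (1 − q)W + q(W − d), so the writers' mean is W = μ + qd. With no true effect and the same d in both arms:

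bias = (qE − qC) × d, where E is the expressive arm and C the control arm.

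The protocol gives neither rates nor gaps, so all of these are assumptions:

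- Equal rates: bias 0.
- Rates 10 percentage points apart, d = 5: 0.10 × 5 = 0.5 points (5% of 11).
- 25% v 10%, d = 10: 0.15 × 10 = 1.5 points (14%).
- Rates 20 percentage points apart, d = 15: 0.20 × 15 = 3.0 points (27%).
- 30% v 5%, d = 15: 0.25 × 15 = 3.75 points (34%).

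The sign reverses if non-writers score higher or if non-writing is commoner in the control arm. The 25% v 10% and 30% v 5% cases both average 17.5%, which is about 23 of 130. That uses most of the 28-person allowance and leaves about 5 for ordinary loss.

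**3. Power if everyone is called.** Assume all 65 per arm are measured and expressive-arm non-writers (fraction w) score like controls. The difference becomes 11 × (1 − w), and power = Φ(difference/(19.56 × √(2/n)) − 1.960) with n = 65 × 0.955 = 62.1.

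| w | Difference | Power |
|---|---|---|
| 0% | 11.0 | 88% |
| 10% | 9.9 | 81% |
| 20% | 8.8 | 71% |
| 30% | 7.7 | 59% |

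Any further loss to follow-up would lower these figures.

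**The case against.** A reader might infer that the protocol makes the primary analysis a writers-only one and that non-writers have no PTGI. The documents do not support that. No section says that non-writers are not called or not analysed. The analysis text compares the two arms, and the aims give the time point without tying it to the writing. Writing at 4 weeks plus the 12 weeks given under Purpose of the Study makes 16 weeks, so timing from enrolment is a possible reading, though not a stated one. The analysis set may also be defined in a statistical analysis plan that is not shown.

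A reader might also infer that everyone who fails to write lacks a follow-up date. That is too broad. A home participant who never returns the text still has the date agreed with the coordinator. Only those who decline, or never schedule a session, have none.

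Two pieces of evidence carry less weight than they seem to. The coordinator's call asks about writing at home, and in-person writing is also allowed, so refusing one is not refusing both. That call also precedes the home instruction sheet, so refusal at that step need not reflect the arm's task. The Risks sentence is a general statement that participation is voluntary; it does not say that stopping the writing ends follow-up.

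Timing from the writing also has a sound reason. Writing may fall 2 to 8 weeks after enrolment, and this starting point keeps the interval from exposure to outcome constant. Aim 1 is itself worded around participating in the intervention.

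These points limit the claim to a risk created by an incomplete rule. They do not fill the gap: both operational descriptions of the call start from the writing, and neither says what to do when there is none. The reason for timing from the writing applies only to those who write, and their timing need not change.

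**Conclusion.** The point holds as a gap in the outcome-collection rule. Followed literally, the rule makes measurement of PTGI, IES-R and HADS depend on a post-randomisation act, and so risks restricting the comparison to writers. It does not establish that the trial plans such a restriction.

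The size of any bias cannot be known from the protocol. It is zero if non-writing is equal across arms and the gap is the same in both. Under the assumed rates and gaps it runs from about 0.5 to 3.75 points, 5% to 34% of the planned 11. The change is worth making because it is cheap and the missing data could not be recovered later. The confidence is moderate, because no non-writing rate is documented and some who refuse to write may refuse the call too.

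**What to change.** In Methods/Procedures: Baseline Assessment and in 4 Month Follow-up, state that every randomised participant is called, whether or not any or all of the writing was done. Time the call from:

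1. the actual writing date;
2. if there is none, the scheduled writing date;
3. if none was set, a fixed interval after enrolment.

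The three-month and four-month statements must be reconciled at the same time, so that a single interval applies. When someone declines or stops the writing, ask separately whether they will still take the call, and count as withdrawn from follow-up only those who refuse it. Analyse everyone who is called in the arm assigned.

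The direct cost is protocol wording, a line in the coordinator's script, some extra calls and the $50 follow-up payment for each. For example, if 10% of 130 did not write, that would be 13 calls and 13 × $50 = $650.

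The larger cost is dilution, which need not be small. On the assumptions above, power is about 81% at 10% expressive-arm non-writing and 71% at 20%. The sponsor should state the non-writing rate it expects and check whether 130 is still enough.
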